9.4.6 Training for participants

A training program for the participants enrolled as provers will be conducted comprising of details of proving process, expectations from provers, maintenance of records, etc. A specific training module will be developed specifically for training of participants.

9.4.7 Coding/randomization

The UIC of the prover will be used for randomization for:

- Inter- individual control: 30% of the provers will be randomized into placebo group
- Intra-individual control: The drug-placebo sequence will be randomized for each prover in the verum group.

Intra-individual control is proposed to be maintained during the proving process to prevent incorrect attribution of symptoms to the IPS^[7].

The randomization will be done using computerized random number charts for allocation to intervention. This list will be used as the basis for the preparation and labeling of the study medication. Intervention allocation will be concealed until the proving is completed and the database has been locked. The sealed randomization list will be stored by the principal investigator and co-investigator at CCRH headquarters.

9.4.8 Blinding

The study will be a double blind study, where the site investigators and the participants at the study site will be kept blind about nature of drug substance and the allocation of participants in the verum and placebo groups. The study medication will be sent in coded forms along with a randomization chart. The nature of the proving substance will be known to the PI and the Co-I/coordinator, but the site investigators and the participants will be blind to the nature of the IPS. The coded study medication will be labeled with the UIC and sent to the proving site.

9. 4.9 Interventions

10.3.1 Arms	Assigned Interventions
Group I : IPS	The verum group will be advised to take the study medication as per schedule. This group will comprise of about 70% of the enrolled participants. The IPS will be given in multiple batches, out of which 1 batch will be placebo and other batches will be IP.
Group II: Placebo	The control group will be given placebo indistinguishable from the study medication. This group will comprise of about 30% of the enrolled participants. Multiple batches will be given, all of which will comprise of placebo.

Both the drug and the placebo will be same in appearance, odor and taste.

9.4.10 Study Medication

Drugs in compliance with pharmacopoeial standards from GMP compliant manufacturers would only be procured. The alcohol to be used as placebo will also be purchased from GMP compliant pharmaceutical firm approved by the Council. The IPS will be prepared in the form of globules of size 30 and will be packed in the form of 1 dram glass bottles, labeled with serial number, prover's code and date of packaging. The placebo will be prepared similarly (dispensing alcohol impregnated globules of size 30) and labeled with serial number, prover's code and date of packaging.

The study medication will be labeled with the following information:

- Study medication protocol-code
- Sponsor: CCRH, India
- Dosage: 4 times xxx a day
- Batches XXX/XXX (batches for both IPS/Placebo production)
- Date:
- Date expiry:
- Subject/randomization No.:

Labeling will take place separately for IPS and placebo. The IPS and placebo medication will be packed in two separate lots/bundles.

The preparation of the IPS/placebo as study medication, for dispensing to individual provers will be done separately to avoid mixing of drugs and placebo batches. This would be done at the pharmacy at CCRH headquarters/CRI, Noida under direct supervision of the PI/coordinator.

9.4.11 Potency for proving

In each proving study, the IPS will be proved in at least 2 potencies used in ascending order.

Pharmacopoeial drugs

The IPS can be proved in dilutions/potencies or tinctures, depending on the safety profile of the drug.

New drugs:

The IPS will be proved in potencies above the identified FSD.

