15. ASSESSMENT OF SAFETY

Safety for the volunteers is an important prerequisite in planning of clinical trials. According to the Basic Principles mentioned in the World Medical Association (WMA) Declaration of Helsinki^[3], "Every medical research project involving human subjects should be preceded by careful assessment of predictable risks and burdens in comparison with foreseeable benefits to the subject or to others. This does not preclude the participation of healthy volunteers in medical research. The design of all studies should be publicly available."

In drug proving, there is no conventional pharmacodynamic action of the drug, because it is administered in high dilutions, which according to experience provokes transient "proving symptoms", but does not cause toxicological effects. Additionally the administration of the IP usually will last only for a short time, which again minimizes the probability of adverse events. All volunteers will be informed about the objectives, potential risks, inconveniences and benefits of the trial and will sign an informed consent form before the beginning of the trial. All changes on the physical and mental levels will be observed.

For identification of adverse events and their management, the HPCUS guidelines^[9] are being adapted.

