24.2 Investigational Proving Substance (IPS)

Drugs with potential to develop pathogenetic effects will be investigational proving substances under the study. Only single drug will be used for proving at a time in a prover.

1. These could be drugs already existing in the Indian/international homoeopathic pharmacopoeias/ formularies.
 - a. These are those drug substances whose basic standardization and safety parameters are known.
 - b. These could include drugs proved and used in homoeopathy or drugs fragmentarily proved, but used in homoeopathy; drugs not proved, but being used in other systems of medicine.

These drugs will be proved in potentized form in different potencies. In case where specific safety data about the drug substance is available for lower dilutions and potencies, the drug can also be used for proving in lower dilutions.

2. New products, with no reported use in homoeopathic system of medicine in any literature will be considered as new drugs. In such a case standardization and safety studies shall be completed before undertaking human proving. The first safe dilution (FSD) would be identified in this case and proving would be conducted only in potencies/dilutions higher than the identified FSD.

In either case, safety and standardization parameters will be recorded and compiled, before initiation of drug proving. The detailed literature review compiling the summary of findings from previous proving & clinical trials known and potential risk and benefits to human subjects will be prepared before initiation of the proving. The drug monograph will reflect the details of the IP including Latin name, chemical name, common names, source, origin, habitat, collection, pharmacognosy, physico-chemical parameters, pharmacological aspects, etc. A certificate of authenticity of this nature will be procured from the manufacturing firm.

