24.3 Placebo

Dispensing ethyl alcohol (used as a vehicle to prepare homoeopathic medicines) soaked pills will be used as placebo. The placebo will also be dispensed in sugar globules of standard size 30. The placebo is indistinguishable from IPS in terms of taste, appearance & smell.

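### Tinctures are allowed in 9.4.11 but not by the IPS definition or the high-dilution safety argument, and the single plain-alcohol placebo is not shown to match them

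*Protocol*

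**What the plan says.** On the form of the IPS, section 9.4.11 states for pharmacopoeial drugs: "The IPS can be proved in dilutions/potencies or tinctures, depending on the safety profile of the drug". For new drugs it is narrower: "The IPS will be proved in potencies above the identified FSD". It also sets a rule for every study: "In each proving study, the IPS will be proved in at least 2 potencies used in ascending order". The operational definition in section 24.2 says of pharmacopoeial drugs: "These drugs will be proved in potentized form in different potencies". It then permits lower dilutions where specific safety data exist. Tinctures are not named there.

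On safety, section 15 reasons: "In drug proving, there is no conventional pharmacodynamic action of the drug, because it is administered in high dilutions". Section 6.1 likewise describes proving as a study of very highly diluted doses that are not toxic.

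On the placebo, section 24.3 fixes one composition: "Dispensing ethyl alcohol (used as a vehicle to prepare homoeopathic medicines) soaked pills will be used as placebo". Section 9.4.10 repeats it for size 30 globules. Section 9.4.9 then asserts, for all studies: "Both the drug and the placebo will be same in appearance, odor and taste". Section 24.3 makes the same claim. No matching agent, sensory check or drug-specific placebo is described.

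**The concern.** There are two problems. First, the protocol does not agree with itself on whether a tincture is an admissible form, and its general safety reasoning presupposes that it is not. Second, the protocol fixes the placebo while leaving the form of the IPS open. Plain alcohol on a globule is a credible match for a high dilution in alcohol. The same claim does not carry over to a tincture or a low dilution.

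Blinding carries much of the weight in this design. Provers write down their own symptoms (9.4.15). The site investigator classifies them and records a view on causality (9.4.16). Symptoms are then separated by drug and placebo (13.4). Section 6.1 says that many provers are students of homoeopathic colleges, who may hold expectations about the outcome. A prover who recognises the arm may report more or different symptoms, and those would enter the drug picture as effects of the IPS.

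**Working it through.** The plan gives no figure to reproduce. The check compares sections and then counts the provers exposed.

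**1. Is a tincture in scope?**
- 9.4.11: yes for pharmacopoeial drugs, subject to the safety profile. For new drugs, only potencies above the first safe dilution.
- 24.2: potentized form, extended to lower dilutions with specific safety data. Tinctures are not mentioned.
- 6.1 and 15: the reasoning assumes ultra-high or high dilution.

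One section admits the form, the definition omits it, and two sections argue from a premise that excludes it. Section 9.4.11 also does not say whether a tincture counts towards the required two potencies.

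**2. Which safeguards remain for a tincture?**
- 9.4.11 makes its use depend on the drug's safety profile.
- 19 makes safety and standardization analysis a precondition of proving.
- 24.2 requires safety parameters to be compiled before proving for both drug classes.
- The safety board in 5.1 is optional and meant for new or non-pharmacopoeial drugs, so it does not cover the class in which tinctures are allowed.

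The high-dilution argument is therefore lost for a tincture, but the prior safety requirements are not.

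**3. How many provers could be affected?**
- Enrolled: 40 (9.3). Allocation: 70% verum, 30% placebo (8, 9.4.7).
- Verum: 40 × 0.70 = 28. Placebo: 40 × 0.30 = 12.
- Minimum of 3 batches (9.4.13), of which 1 is placebo in the verum arm (9.4.9), so 3 − 1 = 2 IPS batches per verum prover.
- Successive batches are separated by a washout of at least 30 days (9.4.17).

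**4. What could a prover recognise?** This depends on how many IPS batches differ perceptibly from plain-alcohol globules. The documents do not say. It also assumes that provers know control batches are all alike.
- Neither IPS batch differs (high dilutions): 0 of 28 learn anything.
- One differs, for example a low form followed by a high potency: the odd batch is IPS, so the arm can be recognised. The other IPS batch and the placebo batch still look alike, so the placebo batch is not identified.
- Both differ: the arm can be recognised, and only here might the placebo batch stand out as well.

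The range for recognising the arm is 0 to 28 of 40. The resulting bias in symptom reports cannot be computed from the documents.

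**The case against.** The strongest reply is that tincture use is optional, confined to pharmacopoeial drugs and conditional on safety. On this view section 9.4.9 sets identity of drug and placebo as a requirement, and how the pharmacy meets it is operational detail. Both arms receive size 30 globules, and no document gives the colour, smell or taste of a medicated globule. The conflict with 24.2 would then come down to one word.

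Much of this stands. A reader might infer that safety is wholly unsupported for tinctures. The documents do not bear that out, because 9.4.11, 19 and 24.2 keep safety conditions in place, and section 15 also relies on short administration and observation. A reader might take the tincture to be undiluted, but the protocol does not say so.

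A reader might also infer that all 28 verum provers would identify their placebo batch and that the 12 controls would infer theirs. Neither follows. Potencies ascend, so only one IPS batch may stand out. Batches are at least 30 days apart and containers are returned (9.6), so any comparison is from memory. Provers are blind to the nature of the IPS (9.4.8), so a control who notices no difference cannot tell whether there should have been one.

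The reply fails on the placebo. Its composition is already fixed in 9.4.10 and 24.3, so 9.4.9 cannot be read as an instruction to match it to each IPS. The identity claim is simply unsupported for a tincture or low dilution.

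**Conclusion.** The point holds as an internal conflict and a conditional threat to blinding, and it should be corrected. Sections 6.1, 9.4.11, 15 and 24.2 do not agree on whether tinctures are in scope, and the high-dilution argument cannot be used for one. The claim that plain-alcohol globules match the IPS has no support for a tincture or low dilution.

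If the globules are perceptibly different, up to about 28 of 40 provers could recognise their arm. That rests on an assumption about perceptibility, which may range from not at all to obvious by substance. For high dilutions the effect is nil. The protocol does not show that the blind fails in any actual study, or that any study has used a tincture. Because it is a generic protocol, however, the gap would recur in every tincture or low-dilution study run under it. No view is taken on which form of the drug is right.

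**What to change.** Reconcile sections 6.1, 9.4.11, 15 and 24.2 so that they agree on whether tinctures are in scope, and say whether a tincture counts as one of the two required potencies. That decision belongs to the sponsor.

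If tinctures stay in scope, amend 9.4.10 and 24.3 for any study using a tincture or a low dilution:
- Match the placebo to that form of the IPS in colour, odour and taste.
- Compare the two side by side at the headquarters pharmacy before coding, and record the result.
- Do not describe the study as double blind if the comparison fails.
- Do not rely on the high-dilution sentence of section 15 for that study. Refer instead to the drug's own safety data, which 24.2 already requires.

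The cost is protocol wording, plus a drug-specific placebo and one check in the affected studies only. The pharmacy that would do the check already prepares the medication. High-dilution studies are unchanged.

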9.4.12 Dosage schedule

Each batch will have 12 doses. The provers will be instructed to take 4 pills, 4 times a day at four hourly interval for 3 days.

In case of drugs which the Council proposes to re-prove considering that the previous proving has generated very few symptoms, the following dosage schedule is proposed:

Day	Number of pills*	Number of doses
1	4	4 times
2	8	4 times
3	12	4 times

* the number of pills taken on each day will be increased consecutively in concordance with the Organon of medicine (Aphorism 129), where in it is mentioned that “a few more globules may be taken”^[6]

9.4.13 Route & Method of administration of IP/placebo

The IPS/placebo will be sent as study medication to the proving site. The study medication will be prepared in batches for each individual prover. A minimum of 3 batches is proposed for one proving. Each batch will comprise of the drug/placebo in globules of size 30. Study medication used in this drug proving will be administered orally as globules, the content of which is allowed to be absorbed orally.

9.4.14 Run -in period

The time period between completion of PME and receipt of medicine batches by the provers at the research centre will be the run in period. This period will be at least 2 weeks and a maximum of 4 weeks. The investigator will hand over provers day book proforma (**Form E**) to the provers. During this period, the prover will be requested to make note of any change in health status and inform the investigator in case of any change in health. The prover will be requested to fill in the provers day book proforma daily and report to the site investigator once a week. During this period, the site investigator will review the provers day book proforma once a week. The run in period will be useful for:

- Allowing site investigator to check on the willingness and ability of the participant to properly complete the diary (those who do not comply would normally be excluded)
- Some of the baseline health characteristics are established, and this can help later with the interpretation and analysis of proving symptoms.

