9.4.16 Data Recording

The prover will be expected to make a daily record of the date and time of intake of study medication in the prescribed proforma. During the 3 day study medication intake period, the prover will report to the investigator daily. The investigator will interrogate the prover about the change in health status/sign and symptoms if any during this period and will record his/her observations in the symptom elaboration proforma (**Form F & G**).

Each symptom must be completed with respect to order of appearance, time of appearance & disappearance, location, sensation/character, modalities, concomitants, direction/extension of symptoms, etc. Clinical examination findings will also be recorded. Appropriate pathological investigations if required would also be advised and the report will be added. For each symptom, the investigator on detailed interrogation with the prover, will classify and mention their symptoms as follows^[9]:

- **NS** - New symptoms, not previously experienced.
- **C-** - Unexpected change representing worsening or aggravation of ongoing or recurring symptoms.
- **C+** - Unexpected change representing an improvement of ongoing or recurring symptoms.
- **RS** - Unexpected recurrence of past symptoms.

The investigator will also record his/her observation about the possible causality of symptoms with the drug intake.

9.4.17 Follow up:

A. If sign(s)/symptoms(s) appear:

- The prover must stop taking the further dose of study medication as soon as he/she feels any change in health status or any sign(s) &/or symptoms(s) develop in accordance with the qualifiers of proving symptoms as described in section 13.2. The investigator will ascertain the qualifiers of the symptom and will advise the prover to stop intake of further doses, once proving symptoms develop.
- The prover notes down the sequence of the appearance of new sign(s) &/or symptoms(s), their progress and the number of doses after which each sign &/or symptom appears with date, time of onset and duration for which it persists. No further dose of the same batch is to be consumed by the prover.
- The prover is expected to report (preferably on a personal visit or telephonically) to the investigator daily (or more frequently) for as long as the symptoms persist.

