Washout period: In such a case, a wash out period of 30 days will be maintained after the last dose of the IP/placebo from the batch has been taken. During this period, the prover will be expected to keep a daily record of his/her health status. The prover will report to the investigator once a week (or earlier in case of development of any symptoms or any change in health status) during which the investigator will interrogate and examine the prover to identify any change in health status. The prover will be expected to record the details of the symptoms as mentioned in 9.4.16 and the investigator is also expected to complete the symptom details as outlined in the same section.

9.4.18 The same procedure is followed till all the batches of the study medication are consumed.

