11.3 Flow chart for proving cycle and study process

12. PROVER PARTICIPATION TIMELINE

[figure not shown]
Day/ Month	0 day	Day 1-7	2 wee ks	Day 1-3 (batc h 1)	no. of days for which symp toms persist	30 days	Day 1-3 (Batc h 2)	no. of days for which symp tom persist	30 da ys	Day 1-3 (Bat ch 3)	no. of days for which symp tom persist	30 da ys	1 week
Screening (Form A)	√												
Informed consent (Form B1 & B2)	√												
PME (History & General Examination) (Form D)		√											
Photograph		√											
Enrollment of prover			√										
Allocation of subject number at CCRH			√										
Run in period			√										
Intervention				√			√			√			
Face to face interview	√	√		√	√		√	√		√	√		√
Telephonic interaction													
Observation period					√			√			√		
Prover daily diary completion (Form E)			√	√	√	√	√	√	√	√	√	√	
Symptom elaboration proforma (Form F)			√	√	√	√	√	√	√	√	√	√	
Washout period						√			√			√	
TME (Form D)													√
AE/SAE assessment (Form G)				√	√	√	√	√	√	√	√	√	√

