14. DATA ANALYSIS

14.1 Qualitative analysis:

14.1.1 Symptom selection criteria:

Drug proving data is in the form of symptoms, where there is no measure of efficacy, but description of individual proving symptoms where qualitative research evaluation will be applied. The evaluation will be done by compilation of the proving symptoms in different categories, representing a certain probability to be associated with the remedy and therefore are the most important ones for further clinical verification.

Example: a symptom will belong to the remedy with great probability if at least one of the following criteria is met^[5].

- Occurrence of the symptom in two or more volunteers
- Objective, measurable signs corroborating with the symptoms
- Distinct intensity of the symptom
- Occurrence of the symptom several times shortly after administration of the drug
- Recurrence of the symptom several times over the course of a number of days
- Recurrence of the symptom using different potencies
- Striking, singular, uncommon symptoms
- Striking, seldom or paradox modalities and/or concomitants of the symptom

However, all symptoms including those appearing in lesser number of provers, less distinct or common symptoms will all be included in the proving data. Symptoms, which are not thought to belong to the drug picture, would also be stated, but under separate headings, marked in a specific manner so they are not lost for clinical verification. Such symptoms may be compared with the clinical verification symptoms at a later stage if required.

14.1.2 Characterizing features of proving symptoms:

All provers are to be included in the analyses. The symptoms obtained under verum or placebo must be listed separately. The proving symptoms are identified and their characterizing feature^[9] will be detailed:

- A.** New symptoms with marked severity, duration or frequency
- B.** Ongoing or recurring symptoms present during the proving that have been unexpectedly and markedly improved
- C.** Ongoing or recurring symptoms that have been unexpectedly and markedly worsened
- D.** Symptoms that recur from the past but have not occurred in the 12 months preceding the proving
- E.** Symptoms that display alteration with another symptom in a single volunteer in such a way that the alteration is strongly individualizing
- F.** Symptoms associated with modalities or concomitant symptoms occurring in other parts of the same prover

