	2							
	3							
	4							
Day 2	1							
	2							
	3							
	4							
Day 3	1							
	2							
	3							
	4							

PROVER'S SIGNATURE

* Prover must write in own language. Avoid all medical terms. Elaborate the symptom as vividly as possible
 ° Intensity of the symptom: Mark your symptom on a scale of 1 to 10, where 1 is very low/slight and 10 is extremely bothersome

Form F

SYMPTOM ELABORATION PROFORMA

(to be filled by SITE INVESTIGATOR)

INSTITUTE/ UNIT

CENTRAL COUNCIL FOR RESEARCH IN HOMOEOPATHY, NEW DELHI

General instructions:

- Write legibly.
- Do not use any abbreviations.
- Write complete sentences.
- Record verbatim conversation with the prover.
- In table – 1 record the detailed conversation held with the prover “verbatim”. From the symptoms detailed in table – 1 and further clarifications made with the prover, complete each individual symptom in table 2
- Query for all details related to circumstances, environmental factors, climatic conditions.
- Attempt to complete the symptoms in all possible aspects
- Avoid all medical and technical terms. Explain each term used as vividly as possible.
- Identify intensity of symptoms on a VAS scale on a scale of 0-100mm. Attach sheets with VAS scale separately
- Under the heading of classification of symptoms (\$): Classify the symptoms as follows after complete questioning with the prover & taking into consideration the previous recordings made with the prover during the PME & run-in phase:
 - New symptoms, not previously experienced (NS)
 - Unexpected change representing worsening or aggravation of ongoing or recurring symptoms (C-)
 - Unexpected change representing an improvement of ongoing or recurring symptoms (C+)
 - Unexpected recurrence of past symptoms (RS)

Name of the Prover.....Proving Code No. CCRH/.....Batch No.....

Face to face reporting by the prover:

Date	Time	Date	Time	Date	Time

Telephonic reporting by the prover

Date	Time	Date	Time	Date	Time

Table - 1

Date	Time of administration of the drug	Verbatim record of symptoms(s)/ any change in bodily functions/change in mental state experienced by the prover in order of their appearance as detailed by the prover

Symptom segregation, completion & development of chronology of complaints

Table - 2

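### Provers are questioned daily while dosing and weekly otherwise, yet section 14.1.1 counts repeated symptoms soon after dosing as evidence for the remedy without a placebo-batch comparison

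*Protocol*

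**What the plan says.** Contact by period:

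- **Run-in (9.4.14).** "This period will be at least 2 weeks and a maximum of 4 weeks". The prover fills in the diary every day, tells the investigator of any change in health, and reports weekly: "During this period, the site investigator will review the provers day book proforma once a week". The section does not mention active questioning.
- **Intake days (9.4.16).** "During the 3 day study medication intake period, the prover will report to the investigator daily". In addition, "The investigator will interrogate the prover about the change in health status/sign and symptoms if any during this period", and each symptom is worked up on the elaboration form. Form E Part 2 has a line for each of the 12 doses.
- **Washout (9.4.17).** The diary continues and contact returns to weekly: "The prover will report to the investigator once a week (or earlier in case of development of any symptoms or any change in health status"). If symptoms appear, contact becomes daily for as long as they last.
- **Timeline (section 12).** The row "Face to face interview" is blank for run-in and for all three washouts. The telephone row is blank in every column. Form F is ticked in run-in and washouts, and adverse-event assessment in washouts.

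Use of the data:

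- **Section 14.1.1** lists criteria, any one of which makes it highly probable that a symptom belongs to the remedy. One is "Occurrence of the symptom several times shortly after administration of the drug".
- **Form F** has the investigator classify symptoms as new, worsened, improved or recurring after full questioning, "taking into consideration the previous recordings made with the prover during the PME & run-in phase".
- **Section 13.4** removes a symptom only if it is identical in every descriptor under drug and placebo.

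**The concern.** How often a symptom is recorded depends on how often it occurs and on how hard someone looks for it. Here the second factor rises when dosing starts and falls when dosing ends. A mild background complaint is more likely to be drawn out by a daily interview than by a weekly look at a diary, so recorded symptoms can concentrate around dosing whatever the pills contain.

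The timing criterion in 14.1.1 treats that concentration as evidence for the remedy, and it is sufficient alone. The protocol has the means to separate artefact from effect: placebo batches are taken on the same schedule with the same questioning. The criterion does not refer to them. At stake is whether entries in the drug picture reflect the substance or the interview schedule.

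**Working it through.** The plan gives no figure of its own to reproduce.

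**1. Routine contact rates (9.4.14, 9.4.16, 9.4.17).**

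| Period | Routine contacts | Per day |
|---|---|---|
| Intake, 3 days | 3 | 1.0 |
| Run-in, 14 to 28 days | 14/7 = 2 to 28/7 = 4 | 0.143 |
| Washout, 30 days | 30/7, about 4 | 0.143 |

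The ratio is 1/(1/7) = 7. It measures contact, not bias, because the diary is daily in every period.

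**2. What unequal capture does to an inert substance.** Let r be the share of symptoms captured outside intake relative to intake. With a constant true rate, the apparent intake-to-baseline rate ratio is 1/r. The documents give no r, so these values are assumptions:

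- r = 1.0: ratio 1.00
- r = 0.8: ratio 1.25
- r = 0.6: ratio 1.67
- r = 0.4: ratio 2.50

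At an assumed background rate of 0.1 symptoms per day, the chance of at least one recorded symptom in three days is 1 − exp(−0.3) = 26% in intake. In three run-in or washout days it is 1 − exp(−0.3r): 21%, 17% and 11% at r = 0.8, 0.6 and 0.4. This shows the direction of the effect and is not an estimate of its size.

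**3. Whether the equal-questioning comparison is available.** Section 9.4.9 gives each verum prover one placebo batch and the control arm only placebo. At the minimum of 30 provers with 30% control (9.3) and three batches (9.4.13):

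- Substance batches: 21 × 2 = 42
- Placebo batches: 21 × 1 + 9 × 3 = 48

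The comparison can be made on data already collected. Within one verum prover it is only two batches against one, so it has to be pooled across provers, and it will be imprecise for rare symptoms.

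**4. Which baseline to use.** A remedy that comes to mind is to question intensively on three run-in days and use those days as the baseline. For a complaint recurring on average every 14 days, the chance that D days with capture r record nothing is exp(−rD/14):

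- Three days, perfect capture: exp(−3/14) = 81%
- 14-day run-in at r = 0.5, 0.7, 0.9: exp(−0.5) = 61%, exp(−0.7) = 50%, exp(−0.9) = 41%

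The three-day baseline is better only if r is below 3/14 = 0.21. Better questioning should therefore add to the existing baseline, not replace it.

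**The case against.** The strongest reply is that the protocol already evens out most of the difference. Diaries are daily in all periods, any change must be reported early, and contact becomes daily while symptoms last. Weekly contact is thus the minimum for a prover who has nothing to report, and r may be close to 1. This stands as a limit on size. It does not make the periods equal: a self-kept record reviewed weekly is not a daily interview with a form line per dose, and complaints that emerge only on asking are the ones affected.

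A second reply is that randomized placebo batches exist to prevent wrong attribution (9.4.7). That is correct, and a comparison of rates between substance and placebo would not be biased by the schedule. But 14.1.1 does not ask for one, the identity rule in 13.4 removes only exact matches, and the incidence measures in 14.2 use only provers on the substance.

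Three stronger readings are tempting and are not supported:

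- A reader might infer from the timeline that no contact is planned in run-in or washout. The text requires weekly reporting, and the Form F and adverse-event ticks imply investigator activity. The telephone row is blank even in the symptom observation periods, where 9.4.17 allows telephone reporting, so its blanks say nothing particular about run-in or washout. This is a mismatch between table and text.
- A reader might infer that any complaint missed in run-in becomes a new symptom. New means never experienced before, and the pre-trial history and full questioning at classification must miss it too.
- A reader might take the sevenfold contact ratio as the bias. The daily diary rules that out.

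**Conclusion.** The point holds for the timing criterion. Active questioning is more intense on intake days than in the periods around them, so apparent clustering after dosing is possible with an inert substance. Section 14.1.1 accepts such clustering as sufficient evidence without checking it against batches questioned in the same way. The direction follows from the schedule. The size depends on r, which the documents do not give; the ratios of 1.25 to 2.50 above rest on assumed values, and r near 1 would make the effect small.

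The classification as new, changed or recurring is exposed to a lesser degree, because it also draws on the pre-trial history and direct questioning.

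The timeline mismatch is certain and does not depend on the bias argument. The contact schedule and the 14.1.1 rule are both set in the protocol, and no later analysis can recover baseline symptoms that were never elicited. The changes should be made, but the issue does not invalidate the design.

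**What to change.** 1. **Section 14.1.1.** Count the timing criterion only when the symptom's per-batch frequency within a stated post-dose window is higher in batches of the substance than in placebo batches, pooling the verum provers' placebo batch with the placebo arm. Report both frequencies. Cost: a short addition to the text and no new data. Fewer symptoms will meet the criterion, and with few placebo batches the comparison is imprecise, so a small excess should not be over-read.
2. **Section 9.4.14.** At the existing weekly run-in contacts, use the same structured questioning and Form F as on intake days; the timeline already ticks Form F there. Keep the pre-trial history and the full run-in diary as the baseline and add these records to them. Cost: longer interviews at two to four visits already planned.
3. **Section 12.** Reconcile the face-to-face and telephone rows with the weekly reporting required in 9.4.14 and 9.4.17. Cost: an editorial correction.
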